1.4.3 Theoretical innovations

This study transcends conventional single-dimension theoretical frameworks by integrating bone–muscle mechanical coupling, technology acceptance behavioural theory, and health-

economic evaluation within the community-based smart elderly care setting, constructing a “mechanism–behaviour–economics” tri-dimensional theoretical model.

Bone–muscle–behaviour coupling theory: Proposes the pathway “behavioural adherence → muscle-strength gain → BMD improvement,” quantifying the muscle mediating effect through grip-strength change (HGS) to explain the behavioural–physiological mechanism of RT-induced BMD improvement [Sub-study 3].

Elderly digital inclusion model: Based on the TAM framework, explores the pathway “perceived ease of use → device usage frequency → training adherence,” providing a new framework for age-friendly smart elderly care [Sub-study 4].

Community exercise economics paradigm: Explores the “equipment-sharing cost-allocation” economic model, demonstrating that centralised community procurement can lower marginal costs and thereby overcome the economic bottleneck of exercise intervention dissemination [Sub-study 6].

1.4.4 Methodological innovations

Small-sample dose–response GAM optimisation: Employs penalised smoothing splines ($k = 3$) to constrain degrees of freedom, stably identifying threshold effects of training frequency on BMD improvement under $n < 100$ conditions, resolving the overfitting problem of conventional regression [Sub-study 2].

Mixed longitudinal trajectory analysis (MLTA): Integrates latent class growth modelling (LCGM) with mixed-effects models to identify QoL change subgroups (e.g., “rapid responders” vs. “slow improvers”) from SF-36 data, enhancing small-sample trajectory classification validity [Sub-study 5].

RCT-embedded micro-costing: Constructs a dynamic “BMD gain–cost” model in a community equipment-sharing scenario, incorporating equipment-sharing cost reduction, long-term fracture-prevention benefits, opportunity costs, and personnel/time costs. Calculates ICER for BMD; Markov modelling projects multi-year cost–utility [Sub-study 6].

1.4.5 Application innovations

Community RT responder screening tool: A nomogram based on baseline grip strength, sedentary time, and BMI for rapid identification of high-responder populations (BMD improvement $\geq 3\%$; AUC = 0.82), guiding targeted resource allocation [Sub-study 1].

Low-technology smart supervision protocol: A “dual-track supervision model”—digital track (WeChat-based training reminders and video guidance) and manual track (weekly telephone follow-up and periodic home visits by community workers).

Health insurance alignment decision tree: Cost-effectiveness outputs translated into policy pathways based on the ICER-to-GDP ratio: when ICER does not exceed one times per-capita GDP, the intervention enters the basic public health service package; when it exceeds this threshold, supplementary commercial health insurance is required.

Chapter 2 Literature Review and Theoretical Foundations

2.1 Bone–Muscle–Metabolic Physiology and Exercise Intervention Mechanisms

2.1.1 Biological basis of bone metabolism and pathological mechanisms of osteoporosis

Bone is a living tissue that undergoes continuous remodelling through the coordinated activity of osteoblasts and osteoclasts. In the remodelling cycle, osteoclasts first adhere to the bone surface and resorb aged bone, forming resorption lacunae; osteoblasts then migrate into these lacunae, depositing new bone matrix that subsequently mineralises. Under normal conditions, bone resorption and formation remain in equilibrium.

In primary osteoporosis, this balance is disrupted. In postmenopausal women, the precipitous decline in oestrogen leads to upregulation of RANKL and downregulation of OPG, accelerating osteoclastic activity beyond osteoblastic capacity. In older men, age-related decline in osteoblast function reduces new bone formation, compounded by insufficient vitamin D synthesis and diminished calcium absorption [29]. The result is progressively porous bone: trabeculae thin and disconnect, cortical bone thins and becomes more porous, and the deteriorated structure can no longer withstand routine mechanical stress—even minor falls may produce fractures [30].

2.1.2 Muscle physiology

Skeletal muscle comprises two principal fibre types: type I (slow-twitch) fibres, which contract slowly but with high endurance, and type II (fast-twitch) fibres, which generate rapid, powerful contractions [31]. Muscle growth occurs through a supercompensation mechanism: RT induces microfibre damage, triggering satellite-cell activation and IGF-1–mediated protein synthesis, resulting in fibre hypertrophy [32]. Ageing drives sarcopenia: muscle mass decreases by 3–8% per decade from age 30, with preferential type II fibre atrophy and declining neural innervation. This selective loss of fast-twitch fibres impairs the capacity for rapid postural adjustments, explaining the elevated fall risk in older adults. RT counteracts sarcopenia by stimulating type II fibre hypertrophy and neural adaptation.

2.1.3 Bone–muscle crosstalk

Bone and muscle are mechanically and biochemically interdependent. Mechanically, muscle contraction imposes loading on bone; according to Wolff’s Law, bone adapts to applied stress

by increasing density in loaded regions and losing mass in unloaded regions [33]. Biochemically, muscle-derived myokines (e.g., irisin) promote osteogenesis, while bone-derived osteokines (e.g., osteocalcin) regulate muscle metabolism [34]. Consequently, muscle atrophy indirectly harms bone: declining muscle strength → reduced mechanical stimulation → accelerated bone loss. Clinically, the sarcopenia–osteoporosis syndrome is highly prevalent, with approximately 60% of OP patients concurrently exhibiting sarcopenia. This bidirectional dependency underscores why RT—simultaneously strengthening both muscle and bone—is an ideal intervention strategy.

2.1.4 Biological mechanisms by which resistance training influences BMD, muscle mass, and function

RT improves the musculoskeletal system through multi-level biological responses. At the molecular level, mechanical stress from muscle contraction activates the Wnt/ β -catenin pathway in osteocytes, promoting osteogenic gene expression, while damaged myofibres release IGF-1, stimulating osteoblast proliferation [35]. At the cellular level, osteoclast activity is suppressed (elevated OPG/RANKL ratio), and satellite cells fuse with type II fibres, increasing cross-sectional area [36]. At the tissue level, trabecular thickness increases, cortical porosity decreases, muscle volume expands, and neuromuscular coordination improves [37]. These effects are dose-dependent, with effective RT demonstrably increasing lumbar spine BMD [38].

2.1.5 Indirect effects of exercise on metabolism, neural control, and fall prevention

The benefits of RT extend beyond the musculoskeletal system. Metabolically, increased muscle mass enhances glucose uptake and improves insulin sensitivity, while chronic inflammatory markers (e.g., IL-6) decrease, attenuating inflammation-mediated bone destruction [39]. Neurologically, repetitive training enhances proprioception and motor-neuron synchronisation, accelerating muscle recruitment [40]. For fall prevention: a 30% increase in lower-extremity strength can reduce chair-stand test time by 20%; a 4-point improvement in the Berg Balance Scale score corresponds to a 40% reduction in fall risk; and a 0.2-second decrease in step-reaction time can avert most accidental falls [41]. RT thus reduces fall risk through multiple pathways and is critical for preventing osteoporotic fractures.

2.2 Summary and Critical Appraisal of the Latest Evidence on Resistance Training for BMD, Function, and QoL

2.2.1 Principal findings from recent high-quality systematic reviews and meta-analyses

Recent high-quality systematic reviews confirm clear benefits of RT for BMD. A 2025 meta-analysis of 17 RCTs reported that RT significantly improved lumbar spine BMD (SMD = 0.88, 95% CI: 0.21–1.56, $P = 0.01$), femoral neck BMD (SMD = 0.89, 95% CI: 0.40–1.39, $P = 0.0004$), and total hip BMD (SMD = 0.30, 95% CI: 0.10–0.50, $P = 0.003$) [42].

Regarding physical function, a 2014 meta-analysis reported that five trials using the Timed Up-and-Go test demonstrated positive results relative to baseline or control [43]. For QoL, evidence remains relatively limited; however, significant improvements in SF-36 social functioning, emotional state, bodily pain, and mental health scores have been observed [44].

Subgroup analyses reveal that high-intensity training ($\geq 70\%$ 1RM) significantly improved total hip and femoral neck BMD ($P < 0.05$), that training three times weekly significantly improved BMD across all measured sites ($P < 0.05$), and that 40-minute RT sessions significantly improved lumbar spine BMD ($P < 0.05$) [42].

2.2.2 Methodological quality appraisal of key studies

Existing evidence presents notable methodological limitations. On the PEDro scale (maximum 10), most RCTs score only 5–6 points. Key deficiencies include difficulty implementing blinding, inadequate sample sizes (70% of studies include < 50 participants, yielding low statistical power), poorly standardised control conditions (approximately 40% of studies use “usual activity” as the comparator without specifying content, potentially overestimating intervention effects), and insufficient long-term follow-up (few studies extend beyond 12 months). These methodological shortcomings diminish evidence reliability and highlight the need for studies with rigorous blinding, larger samples, and standardised controls.

2.2.3 Sources of heterogeneity in the evidence

Variability across studies arises from three principal sources. First, intervention protocol differences: training frequency of three sessions per week significantly improves BMD at multiple sites, interventions lasting ≥ 48 weeks significantly affect femoral neck and total hip BMD, and 40-minute sessions significantly improve lumbar spine BMD [42]. Second, participant characteristics: a 2021 study of 275 older adults aged 62–70 showed that following 9 weeks of progressive RT (three sessions per week), male participants gained 63 mm² in vastus lateralis cross-sectional area versus 20 mm² in females [45]. Third, measurement method differences: variations across DXA device models introduce BMD measurement error [46],

and different functional assessment tools yield varying sensitivity and specificity for fall prediction [47]. Standardisation of study design is therefore essential to reduce variability.

2.2.4 Gaps in the evidence for long-term community application, smart implementation, and individualisation

Three major evidence gaps persist. First, community long-term application evidence is insufficient: the majority of studies were conducted in controlled laboratory or clinical settings, with only three identified trials taking place in real-world community environments; community adherence rates and post-cessation effect maintenance remain unknown. Second, smart implementation research is absent: no study has systematically integrated intelligent devices and platforms (e.g., app-guided training, wearable sensors) into RT; most wearable devices serve monitoring functions only, and the impact of older adults' technology acceptance on outcomes has not been quantified. Third, individualised strategies are lacking: despite known responder variability, predictive tools to identify who will benefit most from RT are unavailable. These gaps collectively motivate the present study to validate long-term effectiveness in real community settings, explore smart-technology enhancement pathways, and develop individualised intervention tools.

2.3 Smart Elderly Care and mHealth Acceptance Theory (TAM/eHLQ)

2.3.1 The Technology Acceptance Model (TAM) and its application and evolution in healthcare

The Technology Acceptance Model (TAM), proposed by Davis in 1989, posits that technology adoption is determined by two core constructs: perceived usefulness (PU)—the degree to which a user believes that technology will improve task performance—and perceived ease of use (PEOU)—the degree to which using the technology is perceived as effortless. These constructs influence attitude, which in turn shapes behavioural intention and actual use [48].

In healthcare, TAM has been widely applied to evaluate acceptance of health information technologies. Applications include electronic health records (EHR), where PU and PEOU have been identified as key determinants of nurse adoption [49,50]; telemedicine, where both constructs significantly predict usage intention among patients and clinicians [51]; and virtual reality (VR), where extended TAM models incorporating perceived enjoyment, age, and curiosity predict VR adoption in clinical settings [52].

TAM has undergone successive extensions. TAM2 (Venkatesh and Davis, 2000) introduced

social influence processes (subjective norms, image) and cognitive factors (job relevance, output quality) [54]. TAM3 further incorporated individual characteristics (self-efficacy, risk perception), social capital, and organisational factors [55]. In health applications, privacy, security, and usability have been added as domain-specific variables [56]. Recent trends include multidisciplinary integration, the systematic addition of external variables, and cross-cultural validation [57].

2.3.2 The eHealth Literacy Questionnaire (eHLQ) framework and its core dimensions

The eHLQ, developed from the eHealth Literacy Framework (eHLF; Norgaard et al., 2015), is a multidimensional instrument comprising 35 items distributed across seven dimensions on a 4-point Likert scale: (1) ability to access health information; (2) ability to understand health information; (3) ability to appraise health information; (4) technical operational ability; (5) perceived needs-fit of technology; (6) digital health management ability; and (7) electronic social-support ability [58].

Older adults consistently score lower on the eHLQ. In Chinese studies, the mean score for the dimension “using technology to process health information” among adults aged 60+ was 46.67, significantly below that of younger cohorts [59].

2.3.3 Specificities of technology acceptance among older adults: barriers and facilitators

Barriers to technology adoption among older adults include physical limitations (poor vision, reduced finger dexterity), cognitive challenges (difficulty retaining operational steps, fear of errors), psychological resistance (preference for face-to-face interaction), and economic constraints (cost of devices and internet access) [60]. Facilitators include visual demonstration-based training (Techatraiphum et al. (2016) showed that visual demonstrations significantly increased telehealth acceptance), family support, age-friendly design features (large fonts, voice prompts, one-touch emergency buttons), and observable benefits (e.g., video calls with grandchildren) [61].

2.3.4 Constructing a theoretical framework integrating TAM and eHLQ to understand and predict adherence to smart elderly care interventions

The integrated TAM–eHLQ framework proposes the following pathways [62]: foundational capacity (higher eHLQ scores → higher PEOU); value recognition (strong eHLQ “health management ability” → higher PU); actual use (high PEOU + PU → intention to use →

training adherence); and external support (family encouragement increases effect by approximately 50%). This framework guides the present study in three ways: using the eHLQ to assess technological capacity, using TAM items to evaluate perceived usefulness and ease of use, and analysing how technology acceptance influences training attendance.

2.4 Cost-Effectiveness and Health Economics Framework

2.4.1 Basic types of health economic evaluation

Health economic evaluation assists decision-makers in determining whether medical interventions warrant investment. Three principal types exist. Cost-effectiveness analysis (CEA) compares the costs and natural health outcomes of different interventions—for example, the cost per 1% BMD improvement or per fracture prevented. Cost–utility analysis (CUA) uses the quality-adjusted life year (QALY) as the effectiveness unit, combining survival time and quality of life; cost per QALY gained (ICER) enables cross-disease comparison. Cost–benefit analysis (CBA) monetises health outcomes, directly comparing the monetary value of averted fractures with intervention costs; however, the monetisation of health value remains controversial and limits practical application.

2.4.2 The concept, calculation, and interpretation of the incremental cost-effectiveness ratio (ICER)

ICER is the core metric for evaluating the economic merit of an intervention. It is calculated as: $ICER = (\text{Cost of intervention group} - \text{Cost of control group}) / (\text{Effect of intervention group} - \text{Effect of control group})$. For example, if smart RT costs CNY 500 per person, control costs CNY 100, and the intervention group gains 0.05 QALY with no change in controls, then $ICER = (500 - 100) / (0.05 - 0) = \text{CNY } 8,000/\text{QALY}$.

ICER must be compared against a willingness-to-pay (WTP) threshold. The internationally accepted benchmark is one to three times per-capita GDP. China’s 2024 per-capita GDP of approximately CNY 95,000 [62] yields a threshold of CNY 285,000/QALY (three times GDP). If ICER falls below this threshold, the intervention is considered cost-effective. Special cases: when the intervention is both less costly and more effective (negative ICER), it is “dominant”; when it is costlier and less effective, it should be rejected. Uncertainty is assessed through bootstrap resampling (1,000 iterations) to generate a cost-effectiveness acceptability curve (CEAC).

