3.2.6 H6 (Sub-study 6)

Preliminary incremental cost-effectiveness analysis demonstrates that the additional cost per unit BMD gain from the smart RT intervention, relative to usual health education, falls within an acceptable WTP threshold. Specifically, the ICER (per 0.01 g/cm² lumbar spine BMD gain) is expected not to exceed the threshold derived from domestic health-economic evaluation standards, confirming that the intervention achieves an acceptable balance between resource investment and health returns.

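### The funding tree in 1.4.5 gives a funding route to ICERs that fail the cost-effectiveness rule in 2.4.2, and H6 is set in a unit that neither GDP cut can decide

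*Protocol*

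**What the plan says.** Four places in the Protocol bear on the economic decision limit.

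- **Section 2.4.2** gives the general range, "The internationally accepted benchmark is one to three times per-capita GDP", and takes "China’s 2024 per-capita GDP of approximately CNY 95,000". It then adopts only the top of the range: GDP "yields a threshold of CNY 285,000/QALY (three times GDP". The verdict rule follows: "If ICER falls below this threshold, the intervention is considered cost-effective". The one explicit rejection is for the dominated case: "when it is costlier and less effective, it should be rejected".
- **Section 1.4.5** sets out a decision tree that turns the economic result into a funding route. Its lower branch reads "when ICER does not exceed one times per-capita GDP, the intervention enters the basic public health service package", and its upper branch reads "when it exceeds this threshold, supplementary commercial health insurance is required". It names no unit for the ICER, no upper bound and no outcome other than these two.
- **Section 3.2.6 (H6)** expresses the ICER per 0.01 g/cm² of lumbar spine BMD and compares it with a "threshold derived from domestic health-economic evaluation standards". No figure is given. The summary of H6 in 3.1.2 gives none either.
- **Section 2.4.4** (Challenge 3) makes EQ-5D-based QALYs the primary economic analysis, with cost per 0.01 g/cm² as a supplement. Sub-study 6 in 1.4.2 uses a further unit, cost per 1% of BMD.

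**The concern.** There are two separate problems.

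First, the tree in 1.4.5 is meant to carry the cost-effectiveness result into policy, but it does not use the threshold that defines cost-effectiveness in 2.4.2. A programme that fails that threshold is still routed to a payer. Followed literally, the two sections give a reader no consistent conclusion for a high ICER.

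Second, H6 is a listed hypothesis of the trial but has no limit in its own unit, and its unit is not that of the primary economic analysis. As written, H6 cannot be declared met or not met. If it is later aligned with QALYs, the sponsor must still say which GDP multiple decides it. If that is left open until the ICER is known, the more favourable multiple can be chosen.

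At stake are the conclusion on H6 and the policy recommendation that sub-study 6 is meant to support.

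**Working it through.** **Inputs from the Protocol.** Per-capita GDP CNY 95,000, benchmark of one to three times GDP, adopted threshold CNY 285,000/QALY (all 2.4.2); cut at one times GDP (1.4.5); H6 unit 0.01 g/cm² (3.2.6).

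**Step 1: reproduce the plan's figures.**
- 3 × 95,000 = 285,000. This matches 2.4.2.
- Worked example in 2.4.2: (500 − 100)/(0.05 − 0) = 8,000 per QALY. This also matches.

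**Step 2: distance between the cuts.** 1 × 95,000 = 95,000 in 1.4.5 and 285,000 in 2.4.2; ratio 285,000/95,000 = 3.0.

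**Step 3: apply both rules to the same ICER.** Assumption: the ICER in 1.4.5 is per QALY.

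| ICER (CNY/QALY) | Rule in 2.4.2 | Tree in 1.4.5 |
|---|---|---|
| 8,000 | cost-effective | public package |
| 95,000 | cost-effective | public package |
| 190,000 | cost-effective | commercial insurance |
| 285,000 | not cost-effective | commercial insurance |
| 500,000 | not cost-effective | commercial insurance |

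Up to 95,000 the sections agree. Between 95,000 and 285,000 the result is a favourable verdict with a different payer, which is coherent. From 285,000 upwards the verdict is unfavourable and the tree still assigns a payer. The rejection rule in 2.4.2 does not fill this gap, because it covers only a programme that costs more and achieves less.

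**Step 4: can either cut decide H6?** A limit per QALY becomes a limit per 0.01 g/cm² only through an exchange value:

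limit per 0.01 g/cm² = (limit per QALY) × (QALYs per 0.01 g/cm²)

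The Protocol gives no such value. For illustration only, assume 0.001 to 0.05 QALY per 0.01 g/cm²:
- One times GDP: 95,000 × 0.001 = CNY 95, up to 95,000 × 0.05 = CNY 4,750.
- Three times GDP: 285,000 × 0.001 = CNY 285, up to 285,000 × 0.05 = CNY 14,250.

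Across this assumed range the H6 limit varies fiftyfold for a fixed GDP multiple, against threefold from the choice of multiple. The missing limit in H6's own unit is therefore a separate gap, and choosing a multiple would not close it.

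**The case against.** The strongest reply is that the two sections answer different questions. Section 2.4.2 judges cost-effectiveness, while 1.4.5 assigns a payer. A programme at CNY 190,000/QALY can be cost-effective and still fall outside the public package. This stands: a reader might infer that the whole band from 95,000 to 285,000 is contradictory, and the text does not support that. The reply does not cover ICERs at or above 285,000.

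A reader might also infer that H6 lacks a limit because of the gap between one and three times GDP, or that H6 could be declared met at CNY 285,000/QALY. Neither follows. H6 is a ratio per unit of BMD, so no QALY limit applies to it as written. Nor does the text show that H6's domestic threshold is a third, distinct limit; one computed from China's GDP could be what is meant.

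It is fair to add that 1.4.5 states no unit, so reading it per QALY is an assumption, although a GDP multiple matches the per-QALY benchmark in 2.4.2. It is also fair that the Protocol's only worked example, at 8,000/QALY, lies about 12 times below the lower cut (95,000/8,000) and about 36 times below the upper one (285,000/8,000), so both rules agree there. Nothing in the document shows that the trial's ICER will fall in a disputed region. Any probability of cost-effectiveness at the two cuts would rest on invented costs and QALY gains.

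Finally, a statistical analysis plan may give H6 a number, and the planned acceptability curve covers a range of thresholds. Neither removes the disagreement between statements already in the Protocol.

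**Conclusion.** The point holds in two parts. (1) For ICERs of CNY 285,000/QALY or more, 1.4.5 gives a funding route to a programme that 2.4.2 does not call cost-effective. This assumes the tree's ICER is per QALY, which the Protocol should state. (2) H6 has no numeric limit in its own unit and uses a different unit from the primary economic analysis in 2.4.4, so it cannot be decided as written. The two GDP cuts differ exactly threefold (95,000 against 285,000). The consequences are confined to H6 and the policy output of sub-study 6. The inconsistency is worth correcting before data are seen, but it does not touch the randomised comparison.

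**What to change.** - **3.2.6:** restate H6 per QALY to match 2.4.4, keep cost per 0.01 g/cm² as a descriptive result, and name in advance the one GDP multiple that decides H6. As written, 2.4.2 gives three times. If the sponsor prefers the stricter one times, 2.4.2 should be changed to match. Inserting a QALY limit while leaving H6 in BMD units would create a new contradiction.
- **1.4.5:** state that the ICER is per QALY and add an outcome for ICERs at or above the threshold in 2.4.2. With that threshold at three times GDP, the commercial-insurance branch then covers only the range from one to three times.
- **Reporting:** read the planned acceptability curve at both CNY 95,000 and CNY 285,000.

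The cost is wording in these sections and two values from a curve already planned. The restatement presupposes the EQ-5D data that 2.4.4 relies on. The schedule in 3.3.4 lists SF-36 but not EQ-5D, so the source of the utilities should be confirmed at the same time. The downside is a possibly less favourable policy conclusion.
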